9.3.11 Exploratory Sensitivity Analyses

For ACLF course at end of hospitalization, specific organ failure at end of hospitalization, and percentage of new infections at end of hospitalization, a sensitivity analyses will be performed in which treatment effects will be adjusted for treatment group, region (Europe or North America) and 3 ACLF grades (ACLF-1b, ACLF-2, or ACLF-3a) as collected from IWRS by fitting an appropriate Logistic Regression model or by means of the Cochran-Mantel-Haenszel (CMH) test.

9.3.12 Serum Albumin Concentration

Serum albumin concentration is measured at each visit through the Day 90 visit and is measured before and after each PE-A 5% session at each visit during the treatment period.

Albumin level in serum will be listed for each subject and summarized by each scheduled visit for the SMT group. A summary table will present descriptive statistics for original values and change in value from baseline. For SMT+PE-A 5% group, change from baseline to the pre-exchange timepoint will be summarized. Moreover, the difference between pre-exchange and post-exchange within each visit will also be summarized.

Assessments after Liver transplant will be removed from summaries and analysis.

Instituto Grifols, S.A. / Protocol IG1407

9.3.13 Ascites Assessment

Ascites assessment will be collected for each treatment day and follow-up visit. The grade of ascites and refractory ascites will be summarized by visit and by treatment.

10 Safety Analysis

Unless otherwise noted, all Safety listings and summaries will be based on the Safety population.

10.1 Adverse Events

Adverse Events are coded using the MedDRA coding dictionary (a version within 1 year of the data base lock).

A treatment emergent adverse event (TEAE) is defined in section [6.1.6](#). Non-TEAEs and TEAEs will be summarized separately.

A suspected adverse drug reaction (ADR) is an adverse event with causal relationship of “definitely related” or “possibly related”, as classified by the investigator. An adverse reaction (AR) is an adverse event with causal relationship of “definitely related”, as classified by the investigator.

An temporally associated AE is an AE that is temporally associated with PE-A 5% and is identified as an AE that occurs during a PE session, or within 72 hours following after the completion of a PE session. These definitions only apply to subjects in the SMT+PE-A 5% group.

All adverse events, both treatment-emergent and non-treatment emergent, will be included in a listing, with a flag to distinguish whether the event is treatment-emergent.

An overall summary of TEAEs will present the number of TEAEs, and the number and percentage of subjects with TEAEs, in the following categories:

- Non-TEAE (AE with Onset Prior to Treatment)
- TEAE
- Suspected ADR
- AR
- TEAE Leading to Death
- Serious TEAE
- Serious Suspected ADR
- Non- Serious Suspected ADR
- Serious AR
- Non-Serious AR
- Non-Serious TEAE
- TEAE Leading to Drug Interruption
- TEAE Leading to Drug Withdrawal
- TEAE Leading to Study Withdrawal
- Temporally Associated TEAEs

In addition, TEAEs will be summarized in the following ways:

- SOC / PT – summary of number of TEAEs and number/percentage of subjects with at least one TEAE by treatment, SOC, and preferred term
 - A select subset of TEAE summaries will also include number of events by SOC and preferred term
- SOC/PT/Severity – summary of number of TEAEs and number/percentage of subjects with at least one TEAE by treatment, SOC, preferred term, and severity

Instituto Grifols, S.A. / Protocol IG1407

- SOC / PT / Causality – summary of number of TEAEs and number/percentage of subjects with at least one TEAE by treatment, SOC, preferred term, and causality
- PT Rates – summary of the total number of plasma exchange sessions, , the total number of temporally associated adverse events and the rate per plasma exchange session, and the total number and rate of adverse events per week on the study by preferred term.. Rate per week on the study is defined as total number of events divided by total duration of weeks on the study . This summary applies to the SMT+PE-A 5% group only.

At each level of summarization, a subject will only be counted once per SOC or preferred term, using the most severe AE or the AE with the strongest causal relationship to the treatment as applicable. Summary tables will be sorted in descending frequency within the SMT+PE-A 5% group, then descending frequency with the SMT group, and then alphabetically.

The following table identifies the sets of adverse events that will be presented for each of these types of summaries.

Adverse Event Subset	TEAE Summary					Listing
	SOC / PT	PT	SOC / PT / Severity	SOC / PT / Causality	PT Rates*	
AEs with Onset Prior to Treatment	x					
TEAEs	X#		x	x	x	x
Suspected ADR	X#		x		x	
Non-Serious Suspected ADR	x					
Serious Suspected ADR	x					
AR	X#		x		x	
Non-Serious AR	x					
Serious AR	x					
TE SAEs	x			x		x
Non-serious TEAEs	x#					
TEAEs leading to Study Withdrawal	x					x
TEAEs leading to Death	x					x
Temporally Associated TEAEs*	x				x	

* This subset applies only to the SMT+PE-A 5% group.

This summary will include number of events by SOC / PT.

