8 ASSESSMENT OF SAFETY

8.1 Safety Variables

- The number of suspected ADRs, including adverse reactions (ARs), and incidence rate of subjects with suspected ADRs during the treatment period and within 72 hours after PE-A 5% completion (or after PE-A 5% stops) will be considered as the main safety variables. The number and incidence rate of overall AEs and SAEs, as well as deaths and discontinuations due to AEs will be also collected and analyzed.
- Vital signs will be recorded at each scheduled visit and in particular before and after each PE-A 5% session.
- Clinical laboratory test parameters (blood cell counts, platelet count, INR, fibrinogen, etc.) will also be assessed according to the study schedule.
- Physical examinations will be assessed according to the study schedule.
- According to the investigator's assessment, all clinically relevant changes in vital function and laboratory testing parameters findings will be considered AEs.

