9.1.3.1 Adverse Events

Adverse events will be coded and classified using MedDRA® terms (system organ class and preferred terms).

When a causal relationship of an AE is classified by the investigator as definitely or possibly related, the event will be defined as a suspected ADR. A suspected ADR with a causal relationship of “definitely related” will be defined as an AR. The sponsor will consider the investigator’s causality assessment and also provide its own assessment. If there is any disagreement in causality assessment between the investigator and the sponsor, a separate summary of suspected ADRs/ARs will be provided.

For summary purpose, AEs will be classified as treatment-emergent AEs (TEAEs) or non-TEAEs depending on the comparison of AE onset date/time with the start date/time of study treatment. A TEAE will be defined as an AE which occurs between the start of study treatment and the final visit of the clinical study. A non-TEAE will be defined as an AE which occurs prior to the start of study treatment. Non-TEAEs and TEAEs will be summarized separately.

In addition, TEAEs, including suspected ADRs, will be summarized by each treatment group, system organ class, preferred term, causal-relationship, severity, and seriousness (serious versus non-serious) using descriptive statistics. At each level of summarization, a

subject will only be counted once per system organ class or preferred term using the most severe AE or the AE with the strongest causal relationship to the treatment.

AEs (including suspected ADRs) temporally associated with PE-A 5% (ie, those occurring during a PE session or within 72 hours after the completion of a PE session) will be summarized by presenting incidences and percentages and listed.

Subjects with SAEs, AEs leading to death, or who withdraw from the study because of an AE will also be individually listed and summarized.

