5.3 Treatment Administration

5.3.1 PE-A 5% Dosage, Procedures, and Treatment Regimen

Plasma exchange treatment (PE-A 5%) will be performed using 5% albumin solution (Albutein 5%). Fresh frozen plasma will be administered after the 5% albumin administration to prevent coagulopathy, and the PE-A 5% session is considered completed at the end of the FFP administration. In subjects without severe coagulopathy (INR ≤ 3), two-thirds of the volume exchanged will be replaced with albumin 5% and one-third with FFP. In subjects with severe coagulopathy (INR >3), half of the volume exchanged will be replaced with albumin and half with FFP.

One-point-two (1.2) plasma volumes will be exchanged per PE-A 5% session. Total blood volume (TBV) will be calculated according to Nadler's formula. Plasma volume will be estimated from the calculated TBV and the Hematocrit (HCT). The volume to be exchanged will be considered as the volume to be infused (not the fluid to be removed).

A minimum of 4 and a maximum of 9 PE-A 5% sessions (maximum treatment period: 17 days) will be performed in each subject. The number of PE-A 5% sessions will be determined by the pattern of response (complete response, no response, or partial response) to PE-A 5% treatment (Table [5-1](#) and Table [5-2](#)) and is described briefly below:

Treatment schedule consists of 2 initial PE-A 5% sessions on consecutive days followed by every other day PE-A 5% sessions. The aim of the intervention is to achieve complete response (resolution of ACLF or improvement to ACLF-1a):

- Subjects with very early complete response after 1 or 2 PE-A 5% sessions (resolution of ACLF or improvement to ACLF-1a) will receive 3 or 2 additional PE-A 5% sessions, respectively, to consolidate the response because the total number of PE-A 5% sessions should not be lower than 4. See Table 4-1 for details.
- Subjects with very early complete response after 3 PE-A 5% sessions (resolution of ACLF or improvement to ACLF-1a) will receive 2 additional PE-A 5% sessions to consolidate the response.
- Subjects with complete response after 4 PE-A 5% sessions (resolution of ACLF or improvement to ACLF-1a) will receive 2 additional PE-A 5% sessions to consolidate the response. See Table 4-1 for details in the protocol.
- Subjects with no response (subject with no change or worsening of ACLF grade) after 4 PE-A 5% sessions will discontinue treatment so the total number of PE-A 5% sessions will be 4.

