5.4.2 Safety Variables

The following safety variables will be assessed in this study:

- **Main Safety Variables**

- The number of suspected adverse drug reactions (ADRs), and adverse reactions (ARs), and incidence rates of subjects with suspected ADRs and ARs for the study period and within 72 hours after PE-A 5% completion (or after PE-A 5% stops).
- The number and incidence rate of overall AEs and Serious Adverse Event(s) (SAEs), as well as deaths and discontinuations due to AEs will be also collected and analyzed.
- According to the investigator's assessment, all clinically relevant changes in vital function and laboratory testing parameters findings will be considered AEs.

- **Other Safety Variables:**

- Vital signs (temperature, blood pressure, heart rate, respiratory rate) recorded at each scheduled visit and in particular before and after each PE-A 5% session
- Clinical laboratory test parameters (blood cell counts, platelet count, INR, fibrinogen, etc.)
- Physical examinations

6 General Statistical Considerations

All analyses will be conducted using SAS Version 9.4 or higher.

Unless otherwise noted, for continuous variables, descriptive statistics for continuous/quantitative data will include the number of non-missing values, mean, standard deviation, median, 25th percentile (Q1), 75th percentile (Q3), minimum, and maximum. In general, the mean, median, Q1 and Q3 will be presented to one decimal place greater than the original data, and the minimum and maximum will have the same number of decimal places as the original data. For categorical/qualitative data, descriptive statistics will include counts and percentages per category.

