8.3 Extent of Exposure to PE-A 5%

For subjects randomized to SMT+PE-A 5%, all exposure details will be listed by visit.

An overall summary of exposure will present the duration of exposure (days), total volume of Albumin 5% exchanged (mL) and number of subjects who missed any scheduled treatment with PE-A 5% per protocol. Duration of exposure in days is defined as (date of last PE-A 5% – date of first PE-A 5% + 1). Interruptions, dose changes, and compliance are not considered in the calculation of duration of exposure.

Exchange interruptions will be summarized by visit. Number of exchanges, number and percentage of exchanges with interruptions, and number and percentage of exchanges with interruptions due to TEAE will be summarized.

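### The 72-hour window for temporally associated AEs opens only at session completion, so AEs starting after an early-stopped plasma exchange session can be missed from those tables and the per-session rate

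*SAP*

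**What the plan says.** The operational rule is in SAP 10.1 and has two parts. For the session itself, the event is "identified as an AE that occurs during a PE session". For the time afterwards, the rule adds an onset "or within 72 hours following after the completion of a PE session". Protocol 9.1.3.1 defines the same set as "those occurring during a PE session or within 72 hours after the completion of a PE session". Neither provides for a session that is not completed.

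Completion has a stated meaning. SAP 5.3.1 says that "the PE-A 5% session is considered completed at the end of the FFP administration", and Protocol 6.1.1.1 says the same.

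The main safety variable is worded more widely. Protocol 8.1 takes suspected adverse drug reactions (ADRs) over the whole of treatment, and for the time that follows it says: "within 72 hours after PE-A 5% completion (or after PE-A 5% stops) will be considered as the main safety variables". SAP 5.4.2 repeats the stopping alternative for suspected ADRs and adverse reactions.

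The schedule in SAP 5.3.1 is "2 initial PE-A 5% sessions on consecutive days followed by every other day PE-A 5% sessions". SAP 8.3 foresees that exchanges may be disturbed by AEs, since the "number and percentage of exchanges with interruptions due to TEAE will be summarized". The temporally associated set feeds a SOC/PT table and, in the PT Rates summary of SAP 10.1, a rate per plasma exchange session. The denominator of that rate is the total number of sessions, with no restriction to completed ones.

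**The concern.** A session halted during the albumin or the FFP never reaches the end of FFP. Applied as written, SAP 10.1 then has no point from which to start the 72 hours. An AE that begins after the stop counts only if it falls in the window of another, completed session or during a later session.

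An example: the FFP of session 1 is halted, no further session is given, and lung injury begins four hours later. The protocol's own description of transfusion-related lung injury (section 5.3.2) reaches to six hours after a blood product. Under the literal rule the event is neither during a session nor within 72 hours of a completion, so it is not temporally associated.

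What is at stake is the count of temporally associated AEs and the per-session rate. A stopped session can add one to the denominator while its post-session period adds nothing to the numerator, which pulls the rate down. SAP 10.1 also holds the only 72-hour AE derivation in the SAP. The suspected ADR and AR tables have no time window, so no other planned output covers the period after a stop that SAP 5.4.2 names.

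**Working it through.** The plan states no figure on this point, so there is none to reproduce. The check has two parts.

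**Wording side by side**

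| Place | Events covered | 72 hours run from |
|---|---|---|
| Protocol 8.1 | suspected ADRs | completion, or stop |
| SAP 5.4.2 | suspected ADRs and ARs | completion, or stop |
| Protocol 9.1.3.1 | AEs, including suspected ADRs | completion of a session |
| SAP 10.1 | AEs | completion of a session |

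The mismatch therefore exists within the protocol and again within the SAP.

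**Hours left uncovered after an early stop**

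Inputs:
- Session days 1, 2, 4, 6, 8, 10, 12, 14 and 16 (SAP 5.3.1 and Table 5-2), so the gap is 24 h between sessions 1 and 2 and 48 h after that.
- Window of 72 h (SAP 10.1).
- Session length D is not given; assumed 0 to 6 h.
- Further assumptions: same start time each day, stop at D/2, all other sessions completed.

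Let g be the gap before the stopped session and h the gap after it. Count time from the start of the stopped session. The period of interest runs from D/2 to D/2 + 72. The previous session's window ends at 72 + D − g. If treatment continues, coverage resumes at h.

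*Treatment ends at the stopped session.* Uncovered = (D/2 + 72) − (72 + D − g) = g − D/2.
- Session 1 has no earlier window: 72 h.
- Session 2, g = 24: 24 − 0 = 24 h down to 24 − 3 = 21 h.
- Sessions 3–9, g = 48: 48 − 0 = 48 h down to 48 − 3 = 45 h.

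*Treatment continues.* Uncovered = h − (72 + D − g) = g + h − 72 − D, or 0 if negative.
- Session 1, no earlier window, h = 24: 24 − D/2 = 24 h down to 21 h.
- Session 2, g = 24, h = 48: 72 − 72 − D = −D, so 0 h.
- Sessions 3–8, g = h = 48: 96 − 72 − D = 24 h down to 18 h.

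| Stopped session | Treatment ends there | Treatment continues |
|---|---|---|
| 1 | 72 h (100%) | 21–24 h (29–33%) |
| 2 | 21–24 h (29–33%) | 0 h |
| 3–8 | 45–48 h (63–67%) | 18–24 h (25–33%) |
| 9 | 45–48 h (63–67%) | not applicable |

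Percentages are of 72 h, for example 45/72 = 62.5% and 48/72 = 66.7%. The middle column also applies when the stopped session was due to be the subject's last in any case, for example session 4 in a non-responder. If the window also ran from the time of stopping, every cell would be 0 h.

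**The case against.** **SAP 10.1 follows the protocol.** This stands. Its rule matches Protocol 9.1.3.1, so a reader who infers that the SAP removed a protocol safeguard would be wrong. A change to SAP 10.1 alone departs from Protocol 9.1.3.1 and must be recorded as such.

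**Two variables are involved.** Protocol 8.1 and SAP 5.4.2 concern suspected reactions; the temporally associated set ignores causality, and the SAP does not say that one derives the other. This also stands. The gap in the rule is there either way.

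**The stopping clause is ambiguous.** It names no session and may mean the end of the treatment course. That is a fair reading and the clause needs clarifying. Where treatment ends at the stopped session, though, both readings open a 72-hour window and SAP 10.1 does not.

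**The definition of completion may only say that FFP belongs to the session.** A programmer who has also read SAP 5.4.2 could reasonably use the stop time. That is possible, but the rule should not depend on it.

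**Little is lost.** This stands in large part. The reaction that prompts a stop, if it begins during the session, is counted. Windows of neighbouring completed sessions recover much of the time. Every AE from the first exchange to the final visit is a TEAE under SAP 6.1.6 and is tabulated and listed. The affected outputs are descriptive and cover the PE-A 5% arm only, so no test or between-arm comparison changes.

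**Conclusion.** The rule as written in SAP 10.1 and Protocol 9.1.3.1 does not handle a session stopped early, and it does not agree with the main safety variable in Protocol 8.1 and SAP 5.4.2. It can understate the temporally associated AE counts and the per-session rate. It should be corrected, but it is a limited fault.

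Per stopped session, the uncovered time ranges from none (session 2, treatment continuing) to the full 72 hours (session 1, with no further session). These hours rest on the assumed session length of 0–6 h, a stop halfway through and regular start times.

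Three stronger conclusions may suggest themselves and are not supported. The first is that harm disappears from the safety record; it does not, because the events remain TEAEs. The second is that everything after a stopped session is lost; that needs session 1 to be stopped and no session to follow. The third is that sessions are commonly stopped because of reactions. The documents give no frequency of stopped sessions, and the interruptions tabulated under SAP 8.3 are not necessarily early stops. The number of events affected, and so the size of any understatement, is unknown.

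**What to change.** In SAP 10.1, define a temporally associated AE as one with onset from the start of a PE session to 72 hours after that session ended. The end is the end of FFP for a completed session and the recorded stop time for one stopped early. Apply this to every session that enters the denominator of the per-session rate, so that numerator and denominator cover the same sessions. State in SAP 5.4.2 whether the stopping alternative refers to a session or to the treatment course. Record the departure from Protocol 9.1.3.1 in SAP section 12. Reporting the number of sessions stopped early next to the rate would let readers judge how much the rule matters.

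The cost is a short change of wording and a small departure from Protocol 9.1.3.1. Session stop times must be available. A 72-hour rule already needs a session end time, but the documents do not confirm that stop times were collected. SAP section 2 says that the last patient visit has taken place, so the SAP should also state what is used when a stop time is missing, for example the last time recorded for that session.

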9.1.3 Safety Analysis

The safety analyses will be addressed by listing and tabulation of AEs (including suspected ADRs), vital signs, physical assessments, and clinical laboratory tests. Data will be described using descriptive analyses and treatment comparisons will be based on review of descriptive statistics. The safety analyses will be based on the Safety population.

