- Subjects in the SMT group with ACLF-1b, -2, or -3a who maintain or worsen their ACLF grades throughout the treatment period (from Day 1 to Day 7), will be further assessed for up to Day 17 and will be then followed up at Hospital Discharge (if applicable) and on Days 21, 28, 60, and 90.

The Treatment Period will be up to 17 days.

Subjects in both the SMT+PE-A 5% treatment group and the SMT control groups will be followed for 90 days after randomization. During the entire study, the safety of both groups will be monitored by a Data Safety Monitoring Board (DSMB).

See [Figure 1](#) for the overall study schema.

Figure 1: Overall Study Schema

FU: follow up visit

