6.1.6 Adverse Events

AEs will be classified as treatment-emergent AEs (TEAEs) or non-TEAEs based on the comparison of AE onset date/time with the start date/time of study treatment. A TEAE is defined as an AE which occurs between the start of study treatment and the final visit of the clinical study. For the SMT + PE-A 5% treatment group, start of study treatment is defined as an AE occurring during or after the first plasma exchange. For the SMT treatment group, it is assumed that subjects were already receiving SMT per institutional standards at the time of randomization; therefore, the start of study treatment will be defined as an AE occurring at or after randomization.

A non-TEAE will be defined as an AE which occurs prior to the start of study treatment.

An AE with incomplete start date/time will be determined to be a TEAE or non-TEAE using the conservative rule specified in [Appendix 3](#).

Adverse events with missing end date will be considered ongoing.

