6.2 Sample Size

Based on the CANONIC study, the overall 90-day mortality rate is assumed to be about 50% in the whole study population ([3](#), [6](#)). Assuming a potential drop-out rate of 10% and 5% type-1 error for a 2-sided Chi-square test, a global sample size of 380 subjects (190 per treatment group) will allow an 80% statistical power to detect an absolute reduction of 15% (a 35% 90-day mortality rate) in subjects treated with SMT+PE-A 5%.

Alternatively, the sample size was calculated based on the log-rank test as follows. Assuming the 90-day mortality rate is 50% for the control group, or equivalently, the survival rate is 50%, which translates to a hazard rate of 0.0077 assuming an exponential distribution. Using a log-rank test at the two-sided significant level of 5%, a total of 141 events would provide at least 80% power to detect an absolute reduction of 15% in mortality rate (a 35% 90-day mortality rate, or equivalently, a 65% survival rate) in subjects treated with SMT+PE-A 5%. This absolute difference in mortality rates translates to a hazard ratio of 0.6215, or an approximate 38% risk reduction. With all subjects followed for the entire 90-day duration of the study, a total of 332 subjects would be required to obtain 141 events. Assuming a dropout rate of 10%, a global sample size of 370 subjects (185 per treatment group) is required. This sample size calculation was performed using Proc Power with the "Twosamplesurvival" statement in SAS version 9.4.

Taking a conservative approach, the larger of the 2 sample sizes (i.e., the one based on the Chi-square test) will be used to ensure the study has sufficient power.

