10.2 Incidence of Disease-Related Complications

All disease-related complications are collected through day 90 and will be listed.

The number and percentage of subjects with at least one occurrence of each of the following disease-related complications after Day 1 will be presented by treatment and by visit, Anticipated disease progression includes, but not limited to:

- HE – including HE I, HE II, HE III, and HE IV
- Gastrointestinal (GI) Bleeding – including lower GI bleeding and upper GI bleeding
- Portal Hypertension
- Ascites
- Spontaneous Bacterial Peritonitis (SBP)
- Hepatorenal syndrome (HRS) – including Type 1 and Type 2
- Associated organ/system failure(s) – to be defined and summarized as described in [9.3.8](#)

In addition, the number of each type of disease-related complication will be counted for each subject and presented by treatment as a continuous variable and as a categorical variable with categories 0, 1, 2, 3, 4 or more. No analysis of treatment differences will be performed. Each type of HE, Gastrointestinal (GI) Bleeding, Hepatorenal syndrome(HRS) and associated organ/system failures will be counted separately.

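### The adverse-event rate per week is planned for the SMT+PE-A 5% arm only, while whole-study event counts and percentages are shown by arm without allowing for different survival time

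*SAP*

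**What the plan says.** SAP 10.1 plans a summary by preferred term that holds two kinds of rate for the PE-A 5% arm: one per plasma exchange session and one per unit of time. The second is defined as follows: "Rate per week on the study is defined as total number of events divided by total duration of weeks on the study". The same item ends with "This summary applies to the SMT+PE-A 5% group only", and the table of planned summaries repeats the restriction in its footnote.

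The main between-arm displays in 10.1 are of the form "summary of number of TEAEs and number/percentage of subjects with at least one TEAE by treatment, SOC, and preferred term", with variants by severity and causality. The window is the whole study: "A TEAE is defined as an AE which occurs between the start of study treatment and the final visit of the clinical study" (SAP 6.1.6). Both arms "will be followed for 90 days after randomization" (SAP 5.1).

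For complications, SAP 10.2 states that "the number of each type of disease-related complication will be counted for each subject and presented by treatment as a continuous variable", and also as a categorical variable. It adds that the arms will not be formally compared. Protocol 9.1.3 says that "treatment comparisons will be based on review of descriptive statistics".

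One event type is handled differently. SAP 9.3.10 compares new infections in both arms by Poisson regression with log study duration as an offset and a correction for overdispersion. That count includes spontaneous bacterial peritonitis and other infections recorded as complications.

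**The concern.** A subject who dies on Day 20 can contribute events for 20 days, and a survivor for 90. If the treatment works as hoped, the PE-A 5% arm is watched for longer and collects more events at the same underlying rate. A reader of the count and percentage tables could take the surplus for harm. If the treatment raises mortality, the arm is watched for less time and a real excess of events can be hidden, which is the worse error in a safety review.

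The restriction to one arm makes sense for per-session rates, because controls have no sessions. It has no such basis for the per-week rate, because both arms have weeks on study. The SAP accepts the principle for infections and does not carry it over to other adverse events or complications.

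**Working it through.** **Inputs (SAP 6.2).** "Assuming the 90-day mortality rate is 50% for the control group", hazard 0.0077 per day under an exponential distribution; 35% mortality on SMT+PE-A 5%; hazard ratio 0.6215; 141 events. The documents give no adverse-event rates, so the event patterns in steps 3 to 5 are assumptions.

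**1. Reproducing the plan.**
- Hazard = -ln(S)/90: -ln(0.50)/90 = 0.007702 and -ln(0.65)/90 = 0.004786. The ratio is 0.6215, as stated.
- Events for 80% power: 139 (Schoenfeld) and 145 (Freedman), against 141 stated. Power at 141 events is 80.6%.
- 141/0.425 = 332, and 332/0.9 = 369, or 370 when evened to 185 per arm, as stated.

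**2. Mean observed time to death or Day 90** = (1 - S90)/hazard.
- SMT: 0.50/0.007702 = 64.9 days (9.27 weeks).
- SMT+PE-A 5%: 0.35/0.004786 = 73.1 days (10.45 weeks).
- Ratio 1.126.

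Other scenarios give these ratios:
- 50% against 45% mortality: 1.044.
- 50% against 40%: 1.086.
- 10% exponential dropout in both arms at the planned mortality: 1.124.
- Early deaths at the 28- and 90-day mortality of Protocol Table 2-2, with hazard ratio 0.6215: 1.16 (control 34% and 46%) to 1.18 (control 37% and 50%).
- Mortality of the matched controls and the pilot study in Protocol 2.2 (65% against 40%): 1.26.

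**3. Event counts when the true rate is equal in both arms.** Split observed time at Day 17, the end of the longest treatment period, using (1 - exp(-17 x hazard))/hazard:
- Days 1-17: 15.93 and 16.33 days, ratio 1.025.
- Remainder: 64.92 - 15.93 = 48.99 and 73.12 - 16.33 = 56.79 days, ratio 1.159.

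With the early rate k times the later rate, the count ratio is (16.33k + 56.79)/(15.93k + 48.99).

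| Event pattern (assumed) | Count ratio, PE-A 5% to SMT | Pooled per-week rate ratio (count ratio/1.126) |
|---|---|---|
| Constant | 1.126 | 1.00 |
| Early rate 5 times later rate | 1.076 | 0.955 |
| Early rate 10 times later rate | 1.056 | 0.938 |
| All events in Days 1-17 | 1.025 | 0.91 |

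The true ratio is 1.00 in every row. Rates calculated separately for the two periods return 1.00 in each period that has events, because the rate is constant within each period.

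**4. Percentage with at least one event**, constant rate r per day and hazard h: r/(r + h) x (1 - exp(-90(r + h))). At 0.02 per week it is 18.6% against 16.6%; at 0.1 per week, 61.4% against 56.0%; at 0.5 per week, 93.6% against 90.2%. Over the rates tried, the gap is 2 to 6 percentage points.

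**5. Example count.** At 0.1 per week and 190 per arm, 190 x 0.1 x 10.45 = 198 events against 190 x 0.1 x 9.27 = 176.

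**The case against.** Four points on the other side carry weight.

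- **The 12.6% is not a figure of the plan.** A reader might infer that it is, because the hazards are. It also needs a constant event rate to Day 90, which the documents do not give. Treatment ends by Day 17, a main safety variable concerns the 72 hours after PE-A 5%, and Protocol 8.3.3.1 and 8.3.10 keep anticipated disease progression out of the adverse events unless a causal link is suspected. Events may well cluster early. This stands, and the size has to be given as a range.
- **A pooled weekly rate has its own bias.** With early clustering, longer survival adds low-risk weeks to the denominator and flatters the longer-surviving arm. At a five-fold early rate the pooled rate is 4.5% too low while the count is 7.6% too high. At ten-fold the rate has the larger error (6.2% against 5.6%). This stands and shapes the fix.
- **Not every safety table is affected.** A reader might infer that all between-arm displays lack a time basis. Infections have the offset model in 9.3.10. Organ failure, laboratory and vital-sign summaries are by visit, and 10.2 also shows complications by visit. The point concerns the whole-study TEAE tables and the per-subject complication counts.
- **The percentage of all subjects with an event is not an error.** It is a legitimate absolute risk with death as a competing event, and it answers a different question from a rate. Those tables should stay.

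It is also true that safety comparisons are descriptive, so no test or error rate is at risk. But the review of these tables is itself the planned safety comparison, so a distortion in them matters.

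**Conclusion.** The point holds in a limited form. The plan defines a person-time rate and withholds it from the arm that would make it interpretable, while the whole-study TEAE tables and per-subject complication counts are set side by side without person-time.

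At the planned survival difference and equal true event rates, the surplus in the longer-surviving arm is about 2.5% if events fall only in Days 1-17, about 8% if the early rate is five times the later one, and 12.6% if the rate is constant. These figures rest on exponential survival at the planned mortality and on assumed event patterns. The size follows the survival difference: with equal mortality there is no distortion from this source, and with higher mortality on PE-A 5% it reverses. The trial stopped early, so the actual person-time will differ from the design values.

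The effect is modest and descriptive. The documents do not support the readings that the safety comparison as a whole is invalid, or that a single pooled rate would settle the matter.

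**What to change.** In SAP 10.1, confine the restriction to the PE-A 5% arm to per-session rates and temporally associated events. Add events per person-week in both arms for TEAEs, serious TEAEs and the complication types in 10.2, separately for Days 1-17 and for later follow-up. State where person-time starts: TEAEs begin at the first exchange in the PE-A 5% arm and at randomization in the SMT arm (6.1.6), whereas the duration in 9.3.10 runs from randomization in both. Keep the existing count and percentage tables.

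If a rate ratio with a 95% confidence interval is added, allow for overdispersion as in 9.3.10. For 10.2, either show the two rates without a ratio or amend the sentence that rules out any analysis of treatment differences.

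The change needs SAP wording and some table programming, and no new data. If the SAP is not amended again, its section 2 already allows an added analysis, documented as such in the clinical study report.
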